5.5.14 Early study termination

The study can be terminated at any time for any reason by Novartis. The patient should be seen as soon as possible and treated as a prematurely withdrawn patient. The investigator may be informed of additional procedures to be followed in order to ensure that adequate consideration is given to the protection of the patient's interests. The investigator will be responsible for informing IRBs and/or ECs of the early termination of the trial.

6 Visit schedule and assessments

Table 6-1 lists all of the assessments and indicates with an "x" when the visits are performed. A Visit 199 (end of treatment run-in visit) will be completed for all patients who enter the treatment run-in epoch. For patients who discontinue during the treatment run-in epoch Visit 199 will be their discontinuation visit. For patients that are randomized, Visit 199 will be their end of treatment run-in disposition visit and will be performed on the same day as Visit 199/201. Safety monitoring criteria, vital signs and laboratory evaluations for randomization (Visit 201) are reflected at Visit 199/201 in Table 6-1.

Patients will have regular clinic visits performed for the first year (up to and including Week 48 [Visit 205]). Thereafter, patients will have clinic visits alternating with telephone contact visits every 12 weeks.

After randomization, study drug discontinuation (permanent or temporary) for any reason does not constitute withdrawal from the study and should not lead to the patient being withdrawn from the study. Patients who discontinue study drug should be requested to return for all of the assessments outlined in Table 6-1 as scheduled. If any patient refuses to return for these assessments or is unable to do so, every effort should be made to contact him/her or knowledgeable informant by telephone to ask if any of the study endpoint events have occurred at the foreseen visit dates for the remaining duration of the study. Documentation of attempts to contact the patient should be recorded in the patient's record.

Visit 201 will be considered the reference visit for all study visits during the randomized treatment epoch. Regardless of the occurrence of any unscheduled visits, scheduled visits should be performed within the specified timeframe in relation to Visit 201 as outlined in Table 6-1. If a visit is completed earlier than scheduled or postponed, it should not result in the next visit being brought forward or postponed.

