6.5.1 Physical examination

A complete physical examination will include the examination of general appearance, skin, neck (including thyroid), eyes, ears, nose, throat, lungs, heart, abdomen, back, lymph nodes, extremities, vascular and neurological. If indicated based on medical history and/or symptoms, rectal, external genitalia, breast, and pelvic exams will be performed.

A short physical exam will include the examination of general appearance and vital signs (BP [SBP and DBP] and pulse). A short physical exam will be conducted at all visits starting from Visit 102 except where a complete physical examination is required (see [Table 6-1](#)).

Information from all physical examinations must be included in the source documentation at the study site. Significant findings that are present prior to signing informed consent must be included in the Medical History part of the CRF. Significant findings made after signing the

informed consent which meet the definition of an AE must be recorded on the AE section of the CRF.

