The post-randomized treatment phase (usually after unscheduled, permanent study drug discontinuation) begins after last study drug intake + 1 day and ends on the date last seen (or vital status confirmed by indirect contact).

Double-blind (DB) phase (Randomized treatment epoch)

The double-blind phase is the combination of the randomized treatment phase and the post-randomized treatment phase.

Baseline for run-in phase

The treatment run-in baseline is defined as the last available measurement prior to or at time of Visit 101 or Visit 102, whichever is earlier. For some parameters, values may be only collected at screening (Visit 1). For them the treatment run-in baseline will be at screening.

Baseline for double blind phase

The baseline for the double blind phase is defined depending on the parameter considered. In general, the baseline for the double blind phase is defined as the last available measurement during the LCZ696 *run-in* phase and randomization (generally Visit 199 or Visit 201). For the parameters that are not designated to have measurements collected during the LCZ696 run-in or randomization, the run-in baseline may be used as the baseline for the double blind phase. The following parameters will have the double blind phase baseline at randomization visit:

NYHA class, HF signs and symptoms, vital signs, waist/hip circumference, eGFR, safety laboratory values, endpoints, 1st morning urine (sub-study patients only), lab assessments, patient global assessment (it is assumed that patients will assess their health status comparing to that at randomization), KCCQ scores and EQ-5D assessments and MMSE.

The following parameters will have their double blind phase baseline measured only at screening visit (Visit 1), i.e., prior or at Visit 101 or 102:

Height, (HF, diabetes, liver, and other) medical histories, demography, echocardiogram, and inclusion/ exclusion criteria.

NT-proBNP will be collected in all patients at Visits 1, 101/102 (whichever occurs first), 103, 199/201, 203 and 205. Additional biological markers will be collected in a subset of patients. For these biomarkers, the baseline will be defined as values at Visit 101 or 102, whichever occurs first.

Unscheduled visit

Only for the analysis of safety laboratory evaluation will unscheduled measurements be taken into account. For efficacy evaluations, measurements from unscheduled visits will generally not be used, unless specifically specified.

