10.2 Analysis for the identified and potential risks in the risk management plan

The identified and potential risks for LCZ696 are listed in [Table 10-2](#). Besides the specifically specified analyses for each risk, which are listed in the table, the following standard analysis will be applied to all risks.

- Incidence (absolute and relative frequency) rates in terms of patient regardless of study drug relationship by treatment group
- Exposure adjusted incidence rates per 100 patient years regardless of study drug relationship, by treatment
- Listing of subject numbers per risk.

The search paths for the related preferred terms (PTs), high level group term (HLGT), high level term (HLT), in Standard Medical Queries (SMQs), or NMQ in MedDRA for the risks in [Table 10-2](#) are store in the [LCZ696 Case Retrieval Strategy \(2019\)](#).

Table 10-2 Identified and potential risks

Risks	Analysis
Hyperkalemia	
 1. Frequency of hyperkalemia leading to treatment interruption and discontinuation regardless of study drug relationship, by treatment 2. Categorical analysis with frequency and percentage by treatment for patients with serum potassium ≥ 5.5 mEq/L, >6.0 mEq/L and >6.5 mEq/L by treatment.
Hypotension	
 1. Blood pressure summary (mean, standard deviation, median, and range) including measurement at each visit and change from baseline will be provided by treatment 2. Summary with frequency and percentage by treatment for patients with: 
 a. systolic blood pressure (SBP) <100 mmHg; b. 30 mmHg drop in SBP;

Risks	Analysis
Angioedema Renal impairment	
c. simultaneous SBP <100 mmHg and 30 mmHg drop in systolic BP.
 
Frequency and percentage by treatment (Standard statistical analysis)
 
 1. Summary for serum creatinine and eGFR by treatment 2. Summary for frequency and percentage by treatment for patients with: 
 a. eGFR decline by >25%, >40%, >50%, and >30 mL/min/1.73 m²; b. Serum creatinine increase by >50%; c. Serum creatinine level >0.5 mg/dL, >2.0 mg/dL, >2.5 mg/dL, >3.0 mg/dL 3. Subgroup analyses on the relationship between eGFR < 60 and ≥60 mL/min/1.73 m² at baseline and incidence rate/severity of AEs/laboratory parameters indicating newly occurred/worsening of renal impairment.
Hypersensitivity	Standard analysis
Anaphylaxis/anaphylactoid reactions	Standard analysis

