10.5 Vital signs

Sitting systolic blood pressure, sitting diastolic blood pressure, sitting pulse rate and body weight will be summarized by treatment group and visit with standard summary statistics (mean, median, standard deviation, min, max), including changes from baseline. Baselines (run-in and double blind period) are defined in [Section 4](#). Graphical mean plots with 95% CIs for these vital signs will also be provided.

The descriptive summaries will be presented by vital sign and treatment group and visit. Change from baseline will only be summarized for subjects with both baseline and post-baseline values and will be calculated as:

- change from baseline = post-baseline value – baseline value

The number and percentage of subjects with clinically notable vital signs changes from baseline will be presented. Clinically notable vital sign results are provided in [Table 10-4](#) below.

Table 10-4 Clinically notable changes in vital signs

Vital Sign (unit)	Clinically notable criteria
Weight (kg)	decrease > 7% from Baseline increase > 7% from Baseline
Sitting systolic blood pressure (mmHg)	<90 and decrease from baseline of >20 >180 and increase from baseline of >20
Sitting diastolic blood pressure (mmHg)	<50 and decrease from baseline of >15 >105 and increase from baseline of >15
Pulse (bpm)	<50 and decrease from baseline of > 15 >120 and increase from baseline of >15

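### Vital signs taken at unscheduled visits are excluded from the value-based hypotension and notable vital-sign counts, although laboratory thresholds in the same risk table use unscheduled values

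*SAP*

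**What the plan says.** SAP Section 4, under the paragraph on unscheduled visits, gives the general rule: "Only for the analysis of safety laboratory evaluation will unscheduled measurements be taken into account". The next sentence covers efficacy: "For efficacy evaluations, measurements from unscheduled visits will generally not be used, unless specifically specified". The allowance for specified exceptions belongs to efficacy only.

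SAP Section 10 lists laboratory evaluations and vital signs as separate parts of the safety evaluation. Blood pressure then appears in two places:

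- SAP Section 10.2, Table 10-2, hypotension row: "Blood pressure summary (mean, standard deviation, median, and range) including measurement at each visit and change from baseline will be provided by treatment", followed by counts of patients with "systolic blood pressure (SBP) <100 mmHg", with a 30 mmHg drop in SBP, or with both together.
- SAP Section 10.5: "The number and percentage of subjects with clinically notable vital signs changes from baseline will be presented". In Table 10-4 the low-SBP criterion is below 90 mmHg with a fall of more than 20 mmHg. Weight is also in that table, with changes above 7% in either direction.

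Separately, SAP Section 10.2 applies a standard analysis to every listed risk, including "Incidence (absolute and relative frequency) rates in terms of patient regardless of study drug relationship by treatment group".

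On collection, Protocol Section 6.5.1 includes SBP, DBP and pulse in the short physical exam and says: "A short physical exam will be conducted at all visits starting from Visit 102 except where a complete physical examination is required". On spacing after the first year, Protocol Section 6 says: "Thereafter, patients will have clinic visits alternating with telephone contact visits every 12 weeks".

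**The concern.** A low reading between scheduled visits is most likely to be taken when the patient comes in because something is wrong. Protocol Section 3.1 allows extra run-in visits to re-check criteria that include SBP and symptomatic hypotension. Protocol Section 6.5.4 refers to unscheduled visits after randomization for tolerability, in the context of local laboratory tests. A rule that ignores unscheduled vital signs removes readings of this kind from counts meant to pick up any occurrence after baseline.

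Hypotension is a listed risk in Table 10-2, and Protocol Section 3.1 names symptomatic hypotension as one of three focuses for dose-level adjustment. A difference between arms is plausible: Protocol Section 1.1 reports greater blood-pressure lowering with LCZ696 than with corresponding valsartan doses in hypertensive patients. Dose level 3 is not part of the run-in (Protocol Section 3.2.4). Outside Japan and India, the first scheduled clinic visit after starting it is Week 4.

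If the counts catch a similar fraction c of affected patients in each arm, the observed absolute difference is c times the true one. The ratio is preserved but the absolute excess is understated. Table 10-2 also becomes harder to read across risks, since its laboratory rows and blood-pressure rows are counted under different rules without a stated reason.

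**Working it through.** The plan gives no figure to reproduce, so the main check is textual.

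**Step 1: does the rule reach vital signs?** Section 4 limits unscheduled values to the safety laboratory analysis. Section 10 treats vital signs as a different item. Vital signs are therefore outside the exception.

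**Step 2: is there an override?** The hypotension row of Table 10-2, Section 10.5 and Table 10-4 do not mention unscheduled readings. The clause allowing specified exceptions applies to efficacy. No override was found, so the general rule stands.

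**Step 3: are there data for the rule to exclude?**

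- Weight: yes. Its row in Protocol Table 6-1 is a clinical-database item marked for the unscheduled visit, and weight is a Table 10-4 parameter.
- Blood pressure: inferred. The short exam is done at all visits from Visit 102 and includes SBP and DBP. The vital-signs row of Table 6-1 is not in the text available for this review, so entry of unscheduled blood pressure in the database could not be confirmed.

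**Step 4: what is unaffected?** Hypotension adverse events found by the MedDRA search enter the incidence and exposure-adjusted rates of SAP Section 10.2. SAP Section 10.3 summarizes hypotension separately as an event of interest and also covers events leading to dose adjustment. Reasons for down-titration are tabulated under SAP Section 7.2.3. Protocol Section 9.5.3 has vital signs listed with notable values flagged. None of these analyses depends on a scheduled reading.

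**Step 5: illustration of visit spacing.**

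- From Protocol Table 6-1: scheduled clinic visits at Weeks 4, 16, 32 and 48, then 72, 96 and so on. The gap after Week 48 is G = 24 weeks, or 12 weeks in Japan, where the telephone contacts are clinic visits.
- Assumed: an episode of L = 1 to 4 weeks starting at a random time in the gap. The range is borrowed from Protocol Section 5.5.5, where it is the recommended time on a lower dose before re-challenge. It is not a stated duration of low blood pressure.

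For L no longer than G, the chance that a scheduled visit falls inside the episode is p = L/G:

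| Gap | L = 1 week | L = 4 weeks |
|---|---|---|
| 24 weeks | 1/24 = 4% | 4/24 = 17% |
| 16 weeks (Weeks 16 to 32, 32 to 48) | 1/16 = 6% | 4/16 = 25% |
| 12 weeks (Weeks 4 to 16; Japan after Week 48) | 1/12 = 8% | 4/12 = 33% |

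Additional visits in Japan within the Weeks 4 to 16 gap would raise capture there.

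**Step 6: what would the change recover?** Let u be the share of otherwise missed episodes that produce an unscheduled visit with a qualifying, databased blood pressure. The gain is (1 - p) x u. At p = 1/24 to 4/24, it runs from zero when u = 0 to 20/24 = 83% or 23/24 = 96% of episodes when u = 1. The documents give no value for u, so the recovered share cannot be narrowed.

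**The case against.** The strongest reply is that clinically important hypotension is already captured. An episode bad enough to prompt a visit or a dose change should be reported as an adverse event. Protocol Section 7.1 collects such events during and between visits, and they are counted under the same risk in Table 10-2. Protocol Section 9.5.3 rests the safety assessment primarily on adverse events, serious adverse events and laboratory abnormalities. This stands, and it limits the point to the value-based counts. It does not remove the point, because adverse-event reporting depends on investigator judgement and the numeric thresholds are there to complement it.

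A second reply is that the different treatment of laboratory values has a rationale. Protocol Appendices 3 and 5 call for repeat potassium and creatinine testing, and no comparable repeat blood-pressure regime is described. Scheduled-only counts also give both arms equal opportunity for detection. This is fair. Two counting rules are not a contradiction in themselves, and it is a good reason to keep the scheduled-only counts beside the wider ones.

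Third, the phrase about all visits in Protocol Section 6.5.1 cannot be literal, since telephone contacts are also visits, and examination findings go to source documents. Database capture of unscheduled blood pressure is therefore an inference. This stands for blood pressure but not for weight.

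A reader might also infer that hypotension prompting an extra visit disappears from the safety report, or that the counts miss most transient hypotension. The documents support neither. The adverse-event route contradicts the first. The second treats the 4% to 17% as a measured loss, when it describes visit spacing under an assumed episode length.

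**Conclusion.** The point holds within limits. As written, SAP Section 4 keeps unscheduled vital signs out of the any-post-baseline threshold counts in Tables 10-2 and 10-4, and at least one databased vital sign, weight, is discarded by it. For blood pressure, the conclusion assumes that unscheduled readings reach the database.

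The direction is clear: short episodes will tend to be undercounted in both arms, while long-lasting hypotension is less affected. The size is unknown, because the documents do not say how often hypotension leads to an unscheduled visit. No efficacy analysis, alpha allocation or adverse-event analysis is touched. This is a cheap improvement, not a threat to the trial's conclusions.

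**What to change.** Amend the paragraph on unscheduled visits in SAP Section 4 along these lines:

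> Safety laboratory evaluations will continue to use unscheduled measurements. For vital signs, the any-post-baseline threshold counts in the hypotension row of Table 10-2 and in Table 10-4 will use all databased post-baseline values from scheduled and unscheduled visits. Means and changes by visit will use scheduled visits only. The threshold counts will also be shown from scheduled visits alone.

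Before finalizing it, confirm from the case report form that blood pressure is entered at unscheduled visits. If it is not, the change helps weight only, and a footnote to both tables should say so.

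The cost is this short amendment, a programming flag and a second set of columns. No additional collection is needed for values already in the database. The downside is that the wider counts depend partly on how often patients attend unscheduled visits, as the laboratory counts already do. Showing both versions lets the reader see how much that matters.

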6.1 Subject disposition

The number and percentage of patients successfully screened will be presented. In addition, the reasons for screen failures will be provided. For patients who are screened more than once, the information from the last screen will be used in the summary. The analysis set is the SCR.

[figure not shown]
The number and percentage of subjects enrolled, completed, and failed in run-in will be summarized for the valsartan run-in and LCZ696 run-in separately. The reasons for run-in failures will be provided. The analysis set is the ENR. The same information for the valsartan run-in phase (VRS) and the LCZ696 run-in phase (LRS) will also be summarized.

[figure not shown]
The number of subjects randomized (RAN) and included in the full analysis set (FAS) will be presented by treatment group. The number and percentage as well as the reasons that subjects had been excluded from the RAN will be summarized by treatment group. The number and percentage of subjects in the FAS who completed the study (“Study completer” see [Figure 6-1](#)), who discontinued the study and the reasons for discontinuation will be presented for each treatment group. The number and percentage of subjects with protocol deviations as well as the criteria leading to exclusion from analysis sets will be presented in separate tables for the FAS.

Study completer is defined as the one died or having vital status available after the close-out date.

Furthermore, the number of subjects enrolled and randomized per region and per country will be presented descriptively for the ENR and the FAS, respectively.

Figure 6-1 Definition of study completer

*: Follow-up means patient’s vital/medical status information. It may be obtained through indirect contact.

As described in [Section 3](#), the disposition analysis will be repeated for the following subgroups:

- Age group <65, ≥65 years
- Age group <75, ≥75 years
- Gender (male, female)
- Race (Caucasian, Black, Asian, Other)
- Region
- Baseline LVEF ≤median, > median

6.2 Background and demographic characteristics

For the run-in phase, summary statistics will be provided by total number of patients based on the ENR for background and demographics, disease characteristics, and cardiovascular risk factors for the run-in phase baseline, including the following parameters: age, age group (<65 years vs. ≥65 years; <75 years vs. ≥75 years), sex, race, ethnicity, weight, height, body mass index (BMI) (mean summary and frequencies in ≤30, >30 and ≤35, and > 35), category of prior CHF medication, prior HF hospitalization, etiology of HF (ischemic vs. non-ischemic), NYHA class, NT-proBNP, BNP, history of MI, history diabetes, history of hypertension, device use, eGFR (mean summary and frequencies in < 60 and ≥ 60), LVEF (mean summary and frequencies in < 50 and ≥ 50), vital signs, and echocardiography parameters. BMI will be calculated as weight (kg) / height² (m²) from the collected height and weight at Visit 1 (Screening Visit).

Similarly, for the double blind phase, summary statistics will be provided by treatment group and total based on the FAS for the above mentioned parameters plus: category of other select cardiovascular medications, duration of heart failure, medical history (including history of MI, diabetes mellitus, hypertension, atrial fibrillation/flutter, stroke). The summary will be based on the data collected at the double blind phase baseline, if available. Biomarkers will use their baseline at Visit 101/102.

Continuous variables will be summarized using n, mean, standard deviation, median, minimum, the first quartile, the third quartile, and maximum. For in-text tables, minimum and maximum will not be presented. Categorical variables will be summarized using frequency and percentage.

As described in [Section 3](#), the background and demographic characteristics analysis will be repeated for the following subgroups and for the FAS:

- Age group <65, ≥65 years
- Age group <75, ≥75 years
- Gender (male, female)
- Race (Caucasian, Black, Asian, Other)
- Region
- Baseline LVEF ≤median, > median

For baseline comparability analysis, categorical variables will be analyzed by Cochran-Mantel-Haenszel Chi-square test ([Fleiss 1981](#)) and continuous variables will be analyzed by F-test. The results of these analyses will be presented in Appendix 16.1.9 only. For categorical variables, the number and percentage of subjects with missing data will be provided but those subjects who are included in the missing category will not be in the denominator for the Cochran-Mantel-Haenszel Chi-square test.

Note that these tests of comparability are performed for descriptive purposes only, and will not serve as a basis for determining entry of explanatory variables into the respective models. However, when these tests yield statistically significant results referring to a p-value less than 0.05, they can be used as supportive information in interpreting the statistical analyses performed on the primary and secondary efficacy variables.

